 - c. Cholinergic drugs, anticholinergic drugs, and antispasmodics
 - d. Psychotropic drugs: Antipsychotics drugs, antidepressants, antimanic drugs, antianxiety drugs, and hallucinogenic agents, etc.
 - e. Steroids (allowed if used in a local application)
 - f. Antithrombotic drugs (antiplatelet drugs and anticoagulants)
 - g. Mucoprotective drugs
- 10) Those who need to take any prohibited concomitant medication during clinical study. (Only Antacid and Prokinetic permitted as rescue drug. The use of Antacid and Prokinetic during the study period will be recorded as subject's prior/concomitant medication)
- 11) Those who took the other investigational product within 4 weeks prior to administration of investigational product.
(But it is possible to enroll in the study [i.e., observational study, retrospective study] that doesn't affect this study's efficacy and safety as determined by the investigator.)

[Laboratory tests]

- 12) At screening, those who had
 - a. serum alanine aminotransferase (ALT), aspartate aminotransferase (AST), or total bilirubin levels $\geq 2 \times$ upper limit of normal
 - b. serum creatinine or BUN $\geq 2 \times$ upper limit of normal

[Others]

- 13) Pregnant or breast-feeding women
- 14) Those who do not consent to use appropriate contraceptive methods during the study.
Appropriate contraceptive methods for patients or their partners:
- For Male subject: to use barrier method such as male condom and surgical sterilization such as vasectomy;
- For Female subject: to use 1) hormonal contraceptive such as Intrauterine system : intrauterine hormone-containing system, implant, injection, contraceptive pills, or 2) non hormonal contraceptive such as Intrauterine system : copper loop,

barrier method : female condom, diaphragm or cervical cap, or surgical sterilization : tubectomy.

15) In the opinion of the investigator, those who were unsuitable for any reason.

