8.5.2.2 Criteria and Method for Adverse Event Assessment

Confirmed information such as occurrence of adverse event (AE), AE term, severity of AE, date of onset and resolution, relationship to the investigational product, action taken, treatment, and outcome will be recorded on the case report form.

Any laboratory abnormality and abnormal finding in physical examination or vital signs that are considered clinically significant will be recorded as AEs.

Adverse event (AE) from the first IP administration to safety follow up visit (visit 4-1 or 5-1) must be recorded regardless of its relationship with the IP. At each visit after IP administration, the following methods may be done to identify AEs:

- Information provided by subject or legal guardian without any prompt
- At each visit, asking open-ended and non-suggestive questions
- Abnormalities observed by the investigator, other medical professionals and relatives.

Except for lost to follow-up, AEs (including AEs unresolved until the completion of the study) will be monitored, if possible, until the AEs recover to the pre-dose state or to the baseline, or the investigator determines that the AEs have normalized or further monitoring is unnecessary.

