8.5.3 Laboratory Tests, Vital Signs, Physical Examination

Results of the laboratory tests, vital signs, physical examination, will be evaluated for changes between before and after the IP administration and changes in normality/abnormality. Any clinically significant change will be recorded as an adverse event on the case report form.

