9.2.4.2 Laboratory Tests, Vital Signs, and Physical Examination

The descriptive statistics (mean, standard deviation, median, minimum, maximum, etc.) will be presented for continuous data, such as hematology, blood chemistry results, and vital signs by treatment group and visit; the frequency and percentage will be presented for categorical data, such as urinalysis, physical examination by category.

For continuous variables, the paired t-test or Wilcoxon signed-rank test for intra-group tests for the difference between Predose (Visit 2 or Visit 1 if there is no Visit 2) and post dose will be conducted to compare the inter-visit differences. The two-sample t-test and Wilcoxon rank sum test will be carried out to compare the difference between the study group and the control group in the changes before and after administration.

For the categorical variables, the McNemar's test will be conducted for the intra-group change (Normal/NCS vs CS), and the Chi-square test or Fisher's exact test will be conducted for the inter-group difference.

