13.8 Expected Adverse Events Caused by the Investigational Product and Precautions for Use

13.8.1 Expected Adverse Events of Fexuprazan

The adverse events predicted from the results of phase 1 and phase 2 studies of Fexuprazan performed so far are as follows.

1) Phase 1 Study (DW_FEXUPRAZAN001)

A dose block-randomized, double-blind, placebo- and active-controlled, single and multiple dosing, dose-escalation clinical phase 1 trial to investigate the safety, tolerability, pharmacokinetics and pharmacodynamics of Fexuprazan after oral administration in healthy male volunteers was conducted. A total of 28 and 35 adverse events occurred in single and multiple dosing studies, respectively, and they were all mild in severity and recovered without any actions taken. Among them, the adverse drug reactions for which possible relationship to the FEXUPRAZAN cannot be ruled out are:

Study	Dose group	Adverse drug reaction term	Severity
Single Dosing Study	FEXUPRAZAN 20 mg	Epigastric discomfort Dyspepsia	Mild Mild
	FEXUPRAZAN 80 mg (fasting)	Headache	Mild
	FEXUPRAZAN 80 mg (fed)	Vomiting (2 events) Headache	Mild Mild
	FEXUPRAZAN 160 mg	Nausea	Mild

Multiple Dosing Study	FEXUPRAZAN 40 mg	Abdominal distension Abdominal pain Skin exfoliation Headache	Mild Mild Mild Mild
	FEXUPRAZAN 80 mg	Blood creatine phosphokinase increased Abdominal discomfort	Mild Mild

2) Phase 2 Study (DW_FEXUPRAZAN002)

A multi-center, randomized, double-blind, active-controlled, phase 2, therapeutic exploratory study was conducted to evaluate the efficacy and safety of Fexuprazan in patients with erosive gastroesophageal reflux disease. The result of safety assessment showed that 63 adverse events occurred in 36 out of 156 subjects who were treated with Fexuprazan, 24 events of which were adverse drug reactions occurring in 13 subjects. Among them, the adverse drug reactions for which possible relationship to the Fexuprazan cannot be ruled out are:

Dose group	Adverse drug reaction term	Severity
FEXUPRAZAN 20 mg	Nausea Abdominal pain Urticaria Oesophageal candidiasis	Mild Mild Mild Mild
FEXUPRAZAN 40 mg	Nausea Abdominal discomfort Headache Erythema Myalgia Feeling abnormal	Mild Mild Mild Mild Mild Mild
FEXUPRAZAN 80 mg	Headache Dizziness (2 events) Rash (2 events) Alanine aminotransferase increased (3 events) Aspartate aminotransferase increased (3 events) Blood lactate dehydrogenase increased Gamma-glutamyltransferase increased Myalgia	Mild Mild Mild Mild Mild Mild Mild Mild

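### Section 9.2.4.2 plans no count of subjects whose post-dose ALT, AST or bilirubin passes a ULN multiple, and its only stated categorical split merges normal values with abnormal values called not clinically significant

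*Combined protocol and SAP*

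**What the plan says.** - **Continuous analysis.** ALT, AST and total bilirubin belong to blood chemistry (Section 8.3.8). Under Section 9.2.4.2, mean, SD, median, minimum and maximum "will be presented for continuous data, such as hematology, blood chemistry results, and vital signs by treatment group and visit". Within-arm change is tested by paired t or signed-rank. Between arms, "The two-sample t-test and Wilcoxon rank sum test will be carried out to compare the difference between the study group and the control group".
- **Categorical analysis.** For categorical variables, "the McNemar's test will be conducted for the intra-group change (Normal/NCS vs CS" is stated, with chi-square or Fisher's exact test between arms. The examples of categorical data are urinalysis and physical examination; liver tests are not named.
- **Stated intention.** Section 8.5.3 says that laboratory results "will be evaluated for changes between before and after the IP administration and changes in normality/abnormality". Section 9.2.4 also bases the safety analysis on laboratory abnormalities.
- **Adverse-event route.** Section 8.5.2.2: "Any laboratory abnormality and abnormal finding in physical examination or vital signs that are considered clinically significant will be recorded as AEs". Section 9.2.4.1 then counts subjects and cases by preferred term and arm.
- **Only ULN multiple.** Exclusion 12 (Section 3.3) bars "serum alanine aminotransferase (ALT), aspartate aminotransferase (AST), or total bilirubin levels" at or above twice the upper limit of normal. It applies at screening only.
- **Earlier data.** Section 13.8.1 lists "Alanine aminotransferase increased (3 events" and the same number for AST among the phase 2 adverse drug reactions at 80 mg.

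**The concern.** A drug effect on liver enzymes may show as a few subjects with clear rises rather than as a shift of the whole arm. To see that pattern a reader needs the number of subjects above a fixed limit, by arm. The plan has no such count.

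Two routes lead to a subject count, the Normal/NCS against CS comparison and the adverse-event table. Both pass through the same clinical-significance call. The documents give no criterion for that call. The trial is open label (Section 4.4) and has no independent data monitoring committee (Section 13.7). A value that moves from normal to abnormal but is called NCS stays in the same cell of the two-level split, so the change in normality announced in Section 8.5.3 is not tabulated on an objective basis.

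At stake is the completeness of the safety report. The primary efficacy conclusion is not affected.

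**Working it through.** **1. Arm size, reproducing the plan's figure.** Section 9.4.2 gives rates of 0.885 and 0.940, margin −0.1, one-sided 2.5%, pooled Z-test. Mean rate = 0.9125.
- SE0 = √(2 × 0.9125 × 0.0875 / 53) = 0.0549
- SE1 = √((0.94 × 0.06 + 0.885 × 0.115) / 53) = 0.0546
- Power = Φ((0.055 + 0.1 − 1.96 × 0.0549) / 0.0546) = 0.807, matching the printed 0.80729.
- 53 / 0.8 = 66.25, so 67 per arm and 134 in total. I use 67, and 53 as the lower case.

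**2. Phase 2 list (Section 13.8.1).** Entries by dose: 4 (20 mg) + 6 (40 mg) + 14 (80 mg) = 24, matching the stated total. The ALT and AST entries are all at 80 mg and all mild. If the three ALT events were three different subjects (an assumption), the rate at 80 mg is at most 3/46 = 6.5%, using the full-analysis-set denominator in Section 1.4.

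**3. What the planned tests do with a few rises.** If k subjects each rise by R × ULN, the arm mean moves by kR/n. For k = 3 and R = 3 this is 9/67 = 0.13 × ULN, or 9/53 = 0.17 × ULN. The documents give neither the SD of change nor the size of a rise, so both are assumed: normal change in all other subjects with SD 0.15, 0.25 or 0.40 × ULN, and 800 simulated trials per setting.

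| Setting (53 or 67 per arm) | t-test p < 0.05 | Rank-sum p < 0.05 |
|---|---|---|
| 3 subjects, rise of 3 × ULN | 15–21% | 6–8% |
| All settings: 3 subjects with rises of 2, 3 or 5 × ULN; 2 subjects with 3 × ULN | 3–22% | 4–8% |

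Simulation error is about √(0.18 × 0.82 / 800) = 1.4 percentage points near 18%.

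**4. The within-arm categorical test.** Three new CS cases and none in the other direction give an exact McNemar p = 2 × 0.5³ = 0.25.

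**5. What a subject count would show.**
- 3/67 = 4.5%, exact 95% CI 0.9% to 12.5%. Against 0/67, Fisher p = 2 × (67 × 66 × 65) / (134 × 133 × 132) = 0.24.
- 3/53 = 5.7%, exact 95% CI 1.2% to 15.7%. Against 0/53, p = 0.24.
- Five against none of 67 gives p = 0.058 and six against none p = 0.028, so six are needed for p < 0.05.

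**6. Why the maximum does not replace the count.** It is one value per arm and visit. Visit 5 covers only subjects in Treatment 2, and withdrawal tests are separate, so by-visit tables do not give each subject's worst post-dose value. An arm with one subject at the maximum and an arm with several close to it can print the same figure.

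**The case against.** Several points against the concern stand.

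- A reader might infer that liver tests are analysed only as group means. They are not: median, minimum, maximum and rank tests are planned, so the largest value in each arm at each visit is reported.
- A reader might infer that marked rises would go unreported. Rises judged clinically significant must be recorded as adverse events and are counted by preferred term. Mild enzyme rises did reach the reaction list in phase 2, although that study was double-blind. Nothing in the documents shows that investigators here would call marked rises NCS, or do so differently by arm.
- A reader might infer a liver signal at the trial dose. The phase 2 events were mild and at 80 mg, twice this dose, and none is listed at 20 or 40 mg. Section 1.4 reports no significant difference in event incidence among groups, and Section 1.6 describes the safety of 40 mg as similar to esomeprazole.
- A reader might take the low power of the planned tests as proof that a count detects more. Step 5 shows that it does not.
- The two-level split is attached to McNemar's test, which needs a binary variable. The frequencies by category and the between-arm test are not expressly limited to it. This leaves the section ambiguous. If the split does not cover chemistry, liver tests have no stated categorical analysis at all. Under neither reading is there a count against a ULN multiple.
- Safety is in the synopsis objective but not in Section 2, and no safety hypothesis is set. This limits the weight of the point.

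**Conclusion.** The point holds as a reporting gap of moderate weight. No count against a ULN multiple is planned after baseline, and the one stated categorical split cannot show a move from normal to abnormal-NCS. What can be lost is the number of subjects with rises called NCS and the number behind each printed maximum.

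The textual finding needs no assumption. The 15–21% and 6–8% figures depend on assumed variability and size of rise; the range over all settings tried was 3–22% and 4–8%. They show that a non-significant mean or rank test says little about a few outlying subjects. They do not show that such subjects will occur, or that a count would reach significance. The documents support tracking a listed adverse drug reaction and do not establish a signal at 40 mg.

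**What to change.** Change Section 9.2.4.2, reporting only, on the safety set, for ALT, AST and total bilirubin:

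1. By arm, give the number and percentage of subjects whose worst post-dose value is above 1 × ULN and at or above 2 × ULN, with exact 95% CIs, irrespective of the CS/NCS call. The second limit is the one in exclusion 12, so for a subject who met that criterion a post-dose value at or above it is a new crossing since screening.
2. Replace the two-level Normal/NCS against CS split with a three-level shift table from baseline to worst post-dose value: Normal, Abnormal NCS, Abnormal CS. This supplies the evaluation named in Section 8.5.3. It also separates subjects who entered between 1 and 2 × ULN from those who rose on treatment.
3. State that worst post-dose means the highest value over Visit 4, Visit 5, Withdrawal and any follow-up test, and that the denominator is subjects with at least one such value.
4. Present both tables descriptively, with no claim of added test power. Keep the planned summaries as support.

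The cost is a wording change and one or two tables from data already collected, with no new tests, visits or subjects and no change to any clinical action. The downside is that mild, non-significant rises become visible in the report.

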9.3 Criteria

Hypothesis: The study group (Fexuprazan 40 mg) is non-inferior to the control group (Esomeprazole 40 mg) in terms of the proportions of subjects with symptoms relief by Week 4.

To determine the noninferiority of the study group (Fexuprazan 40 mg) against the control group (Esomeprazole 40 mg), the **Chi Square test or Fisher's Exact test method** will be used. The lower limit of the 2-sided 95% confidence intervals for the difference between the study group and control group (study group minus control group) will be calculated, and if this lower limit is larger than the non-inferiority margin of -0.1, the study group will be declared non-inferior to the control group.

9.4 Time of Analysis and Rationale for Determination of Sample Size

9.4.1 Time of Analysis

Interim analysis is not planned for this study, and the analysis will be started after the study ends.

9.4.2 Rationale for Determination of Sample Size

This study objective is to determine the non-inferiority of the study group (Fexuprazan 40 mg) compared to the control group (Esomeprazole 40 mg) in patients with erosive gastroesophageal reflux disease. The primary endpoint is the proportions of subjects with symptoms relief at week 4 measured by GERD-Q Score <8 , and the hypothesis is:

$$H_0: \pi_T - \pi_C \leq -0.1 \quad \text{vs.} \quad H_A: \pi_T - \pi_C > -0.1$$

π_T : Proportion of subjects with symptoms relief at week 4 (measured by GERD-Q score <8) in the study group (Fexuprazan 40 mg)

π_C : Proportion of subjects with symptoms relief at week 4 (measured by GERD-Q score <8) in the control group (Esomeprazole 40 mg)

The proportion of subjects with symptoms relief at week 4 of proton pump inhibitors (PPI) was considered to be 88.5%, and this value was set as the proportion of symptoms relief for the control group (Esomeprazole 40 mg). In this study, the proportion of symptoms relief of the study drug was assumed to be higher than control drug, therefore, 94.0% was set as the proportion of symptoms relief in the study group.

The number of subjects calculated by “Non-Inferiority Tests for the Difference Between Two Proportions” of PASS2020 with the non-inferiority margin of -0.1, the one-sided significance level of 2.5%, 80% statistical power, and 1:1 randomization allocation, was 53 per group. And considering a dropout rate of 20%, a total of 134 subjects will be enrolled in the study.

Non-Inferiority Tests for the Difference Between Two Proportions											
Numeric Results											
Test Statistic: Z-Test with Pooled Variance											
Hypotheses: H0: P1 - P2 ≤ D0 vs. H1: P1 - P2 > D0											
Target Power	Actual Power*	N1	N2	N	Ref. P2	P1 H0 P1.0	P1 H1 P1.1	NI Diff D0	Diff D1	Alpha	
0.80	0.80729	53	53	106	0.8850	0.7850	0.9400	-0.1000	0.0550	0.025	
* Power was computed using the normal approximation method.											

10 Data Management (Recording, Collection, Access, Protection, and Storage)

10.1 Data Recording

- 1) The investigator or the person authorized by the investigator should record all data collected in the study on the electronic case report form provided by the sponsor.
- 2) The investigator should record a reasonable explanation for missing data.
- 3) Recorded case report form will be finally signed by the principal investigator.

10.2 Data Collection

The protocol-required data will be collected via the electronic case report form (e-CRF), and all information recorded on the CRF must be consistent with the source document (SD).

Data collection on the CRF must follow the instructions described in the CRF Completion Guidelines.

The investigator has ultimate responsibility for the collection and recording of all clinical data to be entered on the CRF. After completing the CRF, the investigator will assure that information recorded on the CRF is true by signing each CRF. In all cases, the principal investigator must retain full responsibility for the accuracy and authenticity of all data entered on the CRF.

10.4 Protection and Storage of Data

The sponsor and investigator are responsible for retaining clinical study data even after the study completion or termination, and it is mandatory to retain the related clinical documents for at least 3 years since the date of study.

The retention period may be extended if ordered by the Indonesian Food and Drug Authority or determined necessary by the local authorization. The sponsor should inform the investigator and the head of study site about the necessity and duration of data retention in writing. If the sponsor determines that data retention is no longer necessary, they should also inform the principal investigator and the head of study site in writing.

If the PI retires, relocates, or for other reasons withdraws from the responsibility of keeping the study records, custody must be transferred to a suitable alternate custodian employee of the study center or to a suitably qualified and responsible third party. The Sponsor must be notified in writing of the name and address of the new custodian before such transfer is made.

No study records shall be destroyed without notifying and giving the Sponsor the opportunity to arrange long-term storage for such study records or to authorize in writing the destruction of records after the required retention period.

11 Ethical considerations and Administrative Procedures

11.1 Indonesian Good Clinical Practice (CUKB) and Declaration of Helsinki

These protocol-specified procedures are prepared in compliance with international council for harmonization (ICH) good clinical practice (GCP), Indonesian good clinical practice and basic principles of the Declaration of Helsinki for the study sponsor and the investigators to conduct and assess the study and record its result. This study will also be conducted in compliance with national applicable regulations.

11.2 Informed Consent

- 1) The investigator should provide the subjects (or their legally acceptable representative) with detailed explanation of all information about the study and ample opportunities to know all foreseeable outcomes.
- 2) The investigator should provide the subjects with sufficient time to decide whether to participate in this study. Once explanation is provided, the subjects should make their decision in an independent area without the presence of investigators or sub-investigators and should be recommended to make the decision at their next visit, if possible.
- 3) Subject informed consent must be documented. By signing the consent form, the subject agrees to participate in the study and to the collection and use of the subject's personal information in association with the study. The subject's personal information will be used to identify the subject and linked to the clinical data collected during the study. Collected personal information will be coded to avoid identifying individuals and will not be used directly as study data.
- 4) The investigator should confirm by signing the informed consent form. The investigator should not perform any protocol-specific tests before obtaining informed consent from the subjects.
- 5) For vulnerable subjects, the investigator should use an additional informed consent form and obtain consent from them according to the procedures 1) to 4).

11.3 Measures to Protect the Safety of Vulnerable Subjects

"Vulnerable subjects" refers to the subjects whose voluntary decision to participate may be affected by the expectation of benefits associated with the study participation or a concern about possible disadvantage received from senior members of an organizational hierarchy in case of refusal to participate (e.g., a student at college of medicine, Indonesian medicine, pharmacy, dentistry, or nursing, employee of medical institution or research laboratory, employee of pharmaceutical company, soldier, etc.), patients with incurable disease, persons in a collective facility per Article 27 of 'Regulation on the Safety of Pharmaceuticals, etc.', unemployed, poor, patients present in an emergency condition, ethnic minorities, vagrants, homeless, refugees, minors, or subjects who cannot freely give consent.

If employees of the study site, investigator or sponsor, students, etc. wish to participate in the study, their participation in this study will not be limited in order to prevent reverse discrimination against them. The number of vulnerable subjects should not exceed 20% of the total number of subjects. The following should be complied with when recruiting vulnerable subjects.

- 1) The investigators should not interact directly with the employees or students for the purpose of subject recruitment and should not recruit any subjects or conduct the study during work or class.
- 2) Recruitment for the study or informed consent process should be conducted in the absence of senior members of employees or students, if possible.
- 3) Employees or students can decide not to participate in the study, and they should be informed that such decision will not affect their employment, job or grading.
- 4) It should be guaranteed that employees or students will not be unduly influenced or forced and that their privacy will be respected.
- 5) Measures should be taken to ensure that the employee's or student's refusal to participate in the study is not disclosed to their senior members.
- 6) The study should be conducted in the absence of other employees or students, if possible.
- 7) If an employee of the sponsor is recruited as a subject, the identity of the employee should be protected by summarizing all data to be provided to the sponsor, or by removing any personally identifiable information.

